4. OBJECTIVES AND OUTCOME MEASURES

Objectives	Outcome Measures	Timepoint(s) of evaluation of this outcome measure (if applicable)
Primary Objective To demonstrate clinical non-inferiority, followed by superiority, of a shorter antibiotic treatment duration compared to a longer duration in adult patients with VAP	Difference in the proportion of participants with the composite endpoint of death and VAP recurrence rate within 60(± 5) days of enrolment	All outcome measures will be assessed within day 60(± 5) of enrolment
Secondary Objectives To define other clinical benefits of shorter antibiotic treatment duration compared to a longer duration in adult patients with VAP	Ventilator-associated events, duration of mechanical ventilation, duration of hospitalisation, acquisition of multidrug resistant infection or colonisation during the hospitalisation, number of days of exposure to antibiotics during hospitalisation, number and types of extrapulmonary infections during hospitalisation (determined from cultures taken from sterile sites), difference in the proportion of participants with primary outcome in subgroups of patients with VAP caused by Gram-negative non-fermenters and carbapenem-resistant bacilli	All outcome measures will be assessed within day 60(± 5) of enrolment
To study the impact of various antibiotic regimen on the microbial community dynamics and diversity in the respiratory and intestinal tracts in individual patients in order to understand colonisation and transmission of MDROs, identify potentially protective components of the microbiome against MDROs	Characteristics of the microbiota will be determined by comparing alpha and beta diversity metrics between the groups of patients, alterations in the repertoire of antibiotic resistant genes, shifts in microbiota functional and metabolic capacity	Respiratory and stool samples will be collected from the study participants within 24 hours of enrolment, weekly during hospitalisation, and at day 28 (± 5) and 60(± 5) after enrolment

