Respiratory samples (at least 1 set) will be collected from the participants within 24 hours of enrolment, if not yet collected by the managing physician, for microbiological cultures. Respiratory cultures will be collected either via the endotracheal tube (ETT) or bronchoalveolar lavage (BAL) as ordered by the primary physicians. Both non-invasive (ETT) and invasive (BAL) samples are acceptable methods for microbiological diagnosis of VAP. No difference in mortality in the invasive versus non-invasive groups was shown in large randomised controlled studies including the Canadian Clinical Trials study [36], and subsequently a Cochrane meta-analysis [37] of 1,367 patients with VAP. Bacterial isolates grown from all other routine clinical cultures such as blood, cerebral spinal fluid, pus etc, will be retrieved from the microbiology laboratory and frozen and stored. These isolates will undergo whole genome sequencing to compare the within-host evolution of resistant organisms.

For microbiome studies, 1 set of respiratory and stool samples will be collected within 24 hours and weekly during hospitalisation for DNA extraction and microbiome analysis.

We will collect relevant clinical and microbiological data from the participants throughout their hospitalisation. Data collection will be done via review of medical records, microbiological culture results and drug administrative charts.

Concurrently, we will collect prospective data on antibiotics utilisation, adaption and compliance of VAP prevention bundles and hand hygiene rates in the participating units. These audits will include patients

who are not study participants. These data are important as they are potential confounders to our outcome measures including mortality, VAP recurrence rate, duration of mechanical ventilation, acquisition of MDRO infection, and number and types of extrapulmonary infections during hospitalisation. Consents will not be required for these patients not directly participating in the study because these audits are standard procedures in hospitals.

Follow-up visits

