7.5. Baseline Assessments

At recruitment, participants' demographics, medical history, antibiotics administration record, chest X-ray or other imaging findings, biochemical, microbiological and haematological results and clinical parameters will be collected. These are routine investigations ordered by the clinical teams taking care of the patients. Stool samples and upper and lower respiratory tract samples will be collected if they have not already been collected in the 24 hours prior to recruitment.

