2. BACKGROUND INFORMATION

2.1. Objectives

Primary objective

To assess the effect of short (7 days or fewer depending on clinical response) versus long (8 days or more depending on physicians' preference) antibiotic treatment strategies on mortality and pneumonia recurrence within 60 days of enrolment in adults with ventilator-associated pneumonia (VAP) in Asia.

Secondary objectives

To compare the following endpoints according to treatment allocation within 60 days of enrolment:

- a) Ventilator-associated events
- b) Duration of mechanical ventilation
- c) Duration of hospitalisation
- d) Acquisition of multidrug resistant infection or colonisation during the hospitalisation
- e) Number of days of exposure to antibiotics during hospitalisation
- f) Number and types of extrapulmonary infections during hospitalisation (determined from cultures taken from sterile sites)
- g) Adverse events, i.e. antibiotic related diarrhoea, allergic reactions, readmissions

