H_1 : There is a difference in the total duration of mechanical ventilation in the short and long treatment strategy groups, i.e. $t^v_s \neq t^v_l$;

where t^v_s is the duration of mechanical ventilation in the short and t^v_l is the duration of mechanical ventilation in the long treatment strategy groups.

c) Duration of hospitalisation

Definition: Total duration of hospitalisation during the 60 days of follow-up after enrolment.

H_0 : There is no difference in the total duration of hospitalisation in the short and long treatment strategy groups, i.e. $t^h_s = t^h_l$;

H_1 : There is a difference in the total duration of hospitalisation in the short and long treatment strategy groups, i.e. $t^h_s \neq t^h_l$;

where t^h_s is the duration of mechanical ventilation in the short strategy group and t^h_l is the duration of mechanical ventilation in the long treatment strategy group.

d) Acquisition of multidrug resistant infection or colonisation during the hospitalisation

Definition: Growth of multidrug resistant bacteria⁶ from clinically indicated or screening cultures from any source during 60 days of follow-up.

H_0 : There is no difference in the proportion of participants who colonised with multidrug resistant bacteria in the short and long treatment strategy groups, i.e. $\theta^{\text{MDR}} = 0$;

H_1 : There is a difference in the proportion of participants who have ventilator-associated events in the short and long treatment strategy groups, i.e. $\theta^{\text{MDR}} \neq 0$;

where θ^{MDR} is the treatment effect difference between the proportion of participants in the short and long treatment strategy groups.

e) Total number of days of exposure to antibiotics

Definition: Total duration of antibiotic use during the 60 days of follow-up after enrolment.

H_0 : There is no difference in the total duration of antibiotic use in the short and long treatment strategy groups, i.e. $t^a_s = t^a_l$;

H_1 : There is a difference in the total duration of antibiotic use in the short and long treatment strategy groups, i.e. $t^a_s \neq t^a_l$;

where t^a_s is the duration of antibiotic use in the short and t^a_l is the duration of mechanical ventilation in the long treatment strategy groups.

f) Number and types of extrapulmonary infections during hospitalisation (determined from cultures taken from sterile sites)

Definition: Number and types of bloodstream, bone and joint, intracranial, intraabdominal infections during 60 days of follow-up.

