2.7. Outcomes Assessment Schedule

Baseline assessments are performed prior to randomisation on day 0. Other important assessment time points are detailed below.

Time point (Day)	Activity
0	Enrolment, baseline assessments.
Antibiotic prescription	
0-7	Antibiotic choice(s) is / are checked against respiratory endotracheal tube cultures. If current antibiotic choice(s) is / are not appropriate, primary physicians are advised to switch antibiotic choice according

	
to antibiotic susceptibility report (when there is positive growth) or local microbiology antibiogram (when there is no positive growth).
 
Randomisation to short or long treatment strategy. If randomisation is to short arm, all antibiotics for the participant should be stopped on the day of randomisation (other than, when applicable, anti-tuberculosis antibiotics, prophylaxis e.g. peri or post operative or in immunocompromised hosts, gut prokinetic antibiotics)

0 - discharge	Weekly follow-up for new or changes in antibiotic prescription for all participants.
Outcome assessment	
0 - discharge	
New or changes in antibiotic prescription or new respiratory culture reports will trigger screening for pneumonia recurrence. The US CDC VAP diagnostic criteria will be checked during the preceding week.
 
When these diagnostic criteria are met, two independent respiratory or infectious diseases physicians who are blinded to the randomisation arm will be consulted to verify if the episode is a recurrent episode.

0 - 60	
Mortality is assessed weekly.
 
Secondary outcomes such as adverse events, discharge / readmissions, intubation / extubation, clinical cultures, biochemistry laboratory tests are recorded weekly.

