8.7. Acquisition of Multidrug Resistant Infection or Colonisation

Acquisition of multidrug resistant infection or colonisation will be summarised overall and by treatment arm (frequency and percentages). Participants will be categorised as either having or not having acquired multidrug resistant infection or colonisation. Using this as a binary outcome variable, the analysis described in section 7.2 will be repeated.

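### SAP 2.6(d) and 8.7 let multidrug-resistant growth from before randomisation count as acquired; separately, SAP 2.6(b)-(c) and 8.4-8.5 define stay and ventilation differently

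*SAP*

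**What the plan says.** **MDR acquisition.**
- SAP 2.6(d) counts MDR growth "from clinically indicated or screening cultures from any source during 60 days of follow-up". The null hypothesis there compares "the proportion of participants who colonised with multidrug resistant bacteria in the short and long treatment strategy groups". The alternative hypothesis names ventilator-associated events instead.
- SAP 8.7 says only: "Participants will be categorised as either having or not having acquired multidrug resistant infection or colonisation". SAP 8.8, the next section, restricts bloodstream infections to those after randomisation.
- The clock starts at enrolment. The secondary objective in SAP 2.1 is "To compare the following endpoints according to treatment allocation within 60 days of enrolment".
- Protocol section 4 says "Respiratory and stool samples will be collected from the study participants within 24 hours of enrolment, weekly during hospitalisation". Protocol section 5 says that respiratory samples for culture "will be collected from the participants within 24 hours of enrolment, if not yet collected by the managing physician". Protocol 7.5 says that stool and respiratory samples "will be collected if they have not already been collected in the 24 hours prior to recruitment".
- SAP 2.7 puts baseline assessments on day 0, before randomisation, and lists "Randomisation to short or long treatment strategy" under days 0-7.

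**Stay and ventilation.** SAP 2.6(b)-(c) define both as totals within the 60 days after enrolment. SAP 8.4-8.5 analyse two other measures of each. One is time from randomisation to discharge or extubation. The other is time from original admission or intubation to the same end.

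**The concern.** The endpoint's name promises new organisms, but its written definition does not require them. An MDR index pathogen grown from an enrolment sample satisfies the definition before any allocation exists. The same organism grown again later satisfies it too.

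Whether shorter treatment lowers the emergence of resistant organisms is part of the trial's stated rationale (Protocol section 3). Counting organisms that treatment duration could not have caused makes a true reduction harder to see. If persistence or repeat culturing differs by arm, it can also distort the comparison.

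For stay and ventilation, two analysts following different sections of the same SAP would report different quantities under one name.

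**Working it through.** The documents give no rate, effect or power for these endpoints, so there is no stated figure to reproduce. The first step is a reading of the text; the rest is illustration.

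**1. The window.** Origin: enrolment (SAP 2.1). Samples: around enrolment (Protocol sections 4, 5 and 7.5). Randomisation: day 0-7 (SAP 2.7). Growth from specimens taken between enrolment and randomisation therefore lies inside the window. Growth from a specimen taken before enrolment lies outside it, so that organism counts only if it grows again. Two participants with the same index organism can thus be classified differently because of sampling time alone.

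**2. Dilution.** Inputs:
- n = 230 per arm (SAP 2.2), two-sided 5% (SAP 2.6 and 7.3).
- s = 25% and l = 40%: new acquisition in short and long arms. Assumed.
- b: share MDR-positive at baseline. Not in the documents. A rough range from isolate figures in Protocol section 3 is 22% (Singapore, all Gram-negative isolates, carbapenem resistance), and 0.5 × 75% = 37.5% to 0.5 × 95% = 47.5% (Thailand, taking non-fermenters as half of VAP). These are shares of isolates, not participants, with carbapenem resistance standing in for MDR, so they are not bounds.
- c: share of baseline positives who count under the written rule.
- r: carriers' rate of new acquisition relative to non-carriers, 0 to 1.

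With x = s or l:
- Written rule: p = (1−b)x + b[c + (1−c)rx]
- New organisms only: p = (1−b)x + brx

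With c equal in both arms, the new-organism difference exceeds the written one by b·c·r·(l−s), so it is never smaller.

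At b = 37.5%, c = 1: short 0.625 × 0.25 + 0.375 = 53.1%; long 0.625 × 0.40 + 0.375 = 62.5%. Power of the pooled two-proportion test is
Φ{[|p_l − p_s| − 1.96√(2p̄(1−p̄)/n)] / √[(p_s(1−p_s) + p_l(1−p_l))/n]}
= Φ{(0.0938 − 0.0903)/0.0458} = 53%.

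New organisms only: r = 0 gives 15.6% v 25.0%, power 71%; r = 0.5 gives 20.3% v 32.5%, 84%; r = 1 gives 25% v 40%, 93%.

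| b | written rule, c = 1 | new organisms only, r = 0 to 1 |
|---|---|---|
| 22% | 71% | 82-93% |
| 37.5% | 53% | 71-93% |
| 47.5% | 42% | 61-93% |

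Counting everyone (c = 1) is not the worst case: at b = 47.5%, c = 0.75, r = 0, power is 39%.

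**3. Unequal regrowth.** Take b = 47.5%, r = 0. The new-organism rates are 0.525 × 0.25 = 13.1% and 0.525 × 0.40 = 21.0%, a gap of 7.9 points.
- c = 0.5 short, 0.7 long: 13.1% + 23.75% = 36.9% v 21.0% + 33.25% = 54.3%. The gap grows to 17.4 points.
- c = 0.7 short, 0.5 long: 46.4% v 44.8%. The sign reverses.
- No true difference, c = 0.5 v 0.7: 0.475 × 0.2 = 9.5 points of apparent benefit.

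These values of c are assumed; they show only that the direction is not fixed.

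**4. Stay and ventilation, side by side.**

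| | SAP 2.6(b)-(c) | SAP 8.4-8.5 |
|---|---|---|
| Origin | enrolment | randomisation (up to day 7), or original admission/intubation |
| End | 60 days of follow-up | discharge/extubation, no cap stated |
| Readmission, re-intubation | fall within the total | not addressed |
| Death | gives a value, but a shortened one | not addressed |
| Which version leads | one | two, neither named as leading |

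No calculation is needed to show that these differ.

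**The case against.** **The intent is clear from the words.** The endpoint is called acquisition, SAP 8.7 speaks of participants having acquired an organism, and SAP 2.7 separates baseline from outcome assessment. A reader might infer that the sponsor means to count baseline carriage; the documents do not support that. What stands is that the written definition would govern the programming and contains no rule for new organisms, although SAP 8.8 shows that the authors could write such a limit. The alternative hypothesis that names ventilator-associated events looks like a copying slip.

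**Many index isolates may fall outside the window.** Recruitment may follow screening by up to 72 hours (Protocol 7.2). Prior VAP treatment of up to 7 days is not excluded (Protocol 6.3). The cultures that set the antibiotic day count are those within 48 hours of screening or symptom onset (Protocol section 8). The sampling schedule in Protocol section 4 belongs to the microbiome objective, and section 5 sends those samples for DNA extraction, although section 7.7 also mentions stool culture. This stands: c may be well below 1.

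**The numbers rest on assumptions.** This also stands. Neither b nor the acquisition rates come from the documents, and baseline positivity being common is an inference from isolate data.

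**Conclusion.** The point holds as a definitional defect that should be corrected. Followed as written, SAP 2.6(d) counts MDR organisms grown before randomisation as acquired, and neither SAP 8.7 nor the hypotheses prevent this.

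A reader might infer that the rule adds the same events to both arms, so that it can only hide a benefit and never create one. That is right, in expectation, for growth before randomisation only. Regrowth afterwards may depend on antibiotic duration and on how long a participant stays and is cultured, so the bias can run either way.

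A reader might also take 53% v 71-93% as the expected loss of power. It is an illustration at b = 37.5% with every baseline positive counted and new acquisition of 25% v 40%. The actual size is unknown.

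The mismatch for stay and ventilation is plain on the text. Its effect cannot be sized without assuming the mortality gap and the stay distributions.

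All of these are secondary endpoints. Nothing here touches the primary non-inferiority conclusion.

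**What to change.** **SAP 2.6(d) and 8.7.** Count only an MDR organism, defined as species plus resistance phenotype, that is first grown from a specimen taken after randomisation and was not grown from that participant's earlier specimens, including those before enrolment. Keep all randomised participants and state which follow-up cultures count. Report by arm the number with no baseline culture; for them, first growth after randomisation would still count, so the problem remains in part. Correct the alternative hypothesis. Keep any growth as a descriptive result.

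**SAP 2.6(b)-(c) and 8.4-8.5.** Reconcile to one origin, one end and one 60-day cap. State how death, readmission and re-intubation are handled, and show the results beside deaths by arm.

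**Cost.** SAP wording plus the data safety and monitoring committee's approval, which SAP section 4 requires for analysis-plan amendments. Follow-up ended on 14 February 2023 (SAP 2.2) and the statistician is not blinded (SAP 9.2), so the change should be dated and approved before the arms are compared. Otherwise, report the new-organism result beside the written one and label it as added later. Cultures, susceptibility reports and the dates of enrolment, randomisation, discharge, readmission, intubation and extubation are already in the 100% check (SAP section 3). That list names mortality but not the date of death. The main downside is reliance on available baseline cultures: Appendix B of the protocol schedules respiratory culture at day 0 only.

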7.6. Subsequent Visits

Clinical information will be collected during participant's hospitalisation. Two follow-ups will be done on day 28(± 5) and 60(± 5) after recruitment. During these visits, similar clinical information will be collected (if available) via hospital record review. Repeat respiratory and stool sample will also be collected. In the event that the participants are not able to attend the follow-ups in person, a telephone interview can be done in place of a physical visit.

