Patients will be blinded to the study arm they are randomised to, as they will not be informed of the treatment duration and are likely to be sedated and unaware of the treatment regimens. Investigators will be blinded during the assessment of the participants for clinical stability based on the above-described criteria to minimise observer bias. Once conditions for stopping antibiotics are satisfied, the investigator will be unblinded and contact the primary physicians to stop antibiotics. The physicians will remain blinded until they are informed that the participant is suitable to stop antibiotics. Independent assessors, who are assigned to determine pneumonia recurrences, will be blinded from the randomisation arms. This will be achieved by blinding these independent assessors to study details which could be used to determine the allocation arm, including antibiotic treatment, for participants with potential recurrences from.

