5.7. Reliability of Outcome Assessment

As it is not possible to completely blind the treating physicians to the antibiotic treatment duration, we have therefore put in measures for an objective measure of study endpoints. Firstly, all participants are followed up on a weekly interval at the same frequency. Secondly, as the primary outcome measure, all-cause mortality is used. As for pneumonia recurrence, independent assessors are blinded to the randomisation arms by only being provided relevant medical notes which do not contain information on the allocated intervention. Cause of mortality will be determined by the local physicians directly.

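### The MDR acquisition endpoint is ever/never growth from any culture, with no allowance for how many cultures each patient had, so unequal culturing or hospital stay could create or hide a difference between arms

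*SAP*

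**What the plan says.** SAP 2.6(d) defines the endpoint as MDR growth "from clinically indicated or screening cultures from any source during 60 days of follow-up". SAP 8.7 makes it binary: "Participants will be categorised as either having or not having acquired multidrug resistant infection or colonisation". It then repeats the SAP 7.2 analysis. The adjustment covariates listed in SAP 7 are baseline or randomisation-day characteristics. None is a count of cultures, a length of stay or time at risk. SAP 7.7 plans no further sensitivity analysis.

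The cultures that can count come from two sources.

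- **Clinical cultures.** Protocol section 5 says respiratory cultures are taken "as ordered by the primary physicians". SAP 2.4 says that once the stopping conditions are met, "the investigator will be unblinded and contact the primary physicians to stop antibiotics". SAP 5.7 accepts that "it is not possible to completely blind the treating physicians to the antibiotic treatment duration".
- **Scheduled samples.** Protocol section 4 has respiratory and stool samples taken within 24 hours of enrolment, then "weekly during hospitalisation, and at day 28 (± 5) and 60(± 5) after enrolment". Protocol 7.6 adds that, for participants unable to attend, "a telephone interview can be done in place of a physical visit".

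Against incomplete blinding, SAP 5.7 offers three measures: "all participants are followed up on a weekly interval at the same frequency", the use of all-cause mortality, and blinded assessors for pneumonia recurrence.

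**The concern.** An ever-positive outcome depends on how often one looks as well as on whether resistance is present. Here the number of looks is settled after randomisation. Part of it depends on physicians who, for most of the 60 days, can know the arm, and part on how long the patient stays in hospital.

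None of the measures in SAP 5.7 deals with this. Equal weekly follow-up does not give equal numbers of cultures, and blinded assessment covers recurrence only. A route to unequal looks is easy to see. Protocol section 9 recognises that relapse may be more frequent in the short arm, and a suspected relapse is a natural reason to take cultures. A longer stay in either arm adds weekly samples.

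Protocol section 3 asks whether short treatment lowers the emergence of MDR organisms, and this endpoint is the direct patient-level clinical comparison on that question. Under the plan as written, a difference in culturing could be read as a difference in resistance, or could conceal one.

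**Working it through.** **Inputs from the documents.** 230 per arm (SAP 2.2); two-sided superiority test (SAP 2.6); significance level 0.05 (SAP 7.3). The documents give no MDR rate, culture count, culture yield or power for this endpoint, so there is no planned figure to reproduce. All other inputs below are assumptions.

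**Check 1: one extra culture, no true difference.** Let T be the proportion of true carriers, equal in both arms, s the chance that one culture from a carrier is positive, and k the number of cultures. Then

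P(ever positive) = T × [1 − (1 − s)^k].

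Hold the average yield T × s at 25% and compare k = 3 with k = 4. False significance is the probability of two-sided p < 0.05 in a two-proportion test with 230 per arm (pooled standard error for the critical value, unpooled for the spread).

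| T | s | k = 3 | k = 4 | Spurious gap | False significance |
|---|---|---|---|---|---|
| 100% | 25% | 57.8% | 68.4% | 10.5 points | 65% |
| 62.5% | 40% | 49.0% | 54.4% | 5.4 points | 21% |
| 50% | 50% | 43.8% | 46.9% | 3.1 points | 10% |
| 40% | 62.5% | 37.9% | 39.2% | 1.3 points | 6% |
| 31.25% | 80% | 31.0% | 31.2% | 0.2 points | 5% |

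Worked example, second row: 0.625 × (1 − 0.6³) = 0.625 × 0.784 = 0.490, and 0.625 × (1 − 0.6⁴) = 0.625 × 0.8704 = 0.544. The gap is 0.054.

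The first row is the case of fully independent cultures, in which everyone is a carrier and one culture finds it a quarter of the time. The lower rows allow for non-carriers staying negative and carriers testing positive repeatedly. The gap then shrinks quickly.

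**Check 2: one extra week in hospital, same true acquisition.** A simulation gave both arms the same weekly acquisition hazard (0.1 or 0.2) over four weeks whatever the stay, with persistent carriage and detection of 0.4 or 0.7 per sample. Weekly samples were taken for three weeks in one arm and two in the other, and day-28 and day-60 samples were obtained with a set probability.

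| Day-28/60 samples obtained | Spurious gap | False significance |
|---|---|---|
| None | 6.8–13.7 points | 58–87% |
| Half | 3.6–7.6 points | 14–39% |
| All | 1.0–4.2 points | 6–15% |

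The whole gap is artefact here by construction, because acquisition was not allowed to depend on stay.

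**Reference case.** With the same number and timing of counted cultures in both arms, the artefact is 0 points and the test keeps its 5% level.

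**The case against.** A reader might infer that the short arm will be cultured more and that a real benefit will therefore be hidden. The documents do not show this. Nothing in them establishes that either arm is cultured more or stays longer, and weekly follow-up and the day-28 and day-60 visits are the same for both arms. Unequal culturing is a possibility that the analysis leaves open.

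A reader might also take 10.5 points and about 65% as the expected size. Those figures need every patient to be a carrier and every culture to be independent, which is the extreme of the range.

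Nor is a stay-related excess all artefact. The endpoint is headed as acquisition during hospitalisation, more hospital days bring real exposure, and stay may itself be affected by the strategy. SAP 8.4 reports stay by arm, so a difference would be visible. SAP 5.4 reports available against expected data by arm, which would show much of the missing scheduled sampling, though not the number of clinical cultures.

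It would go too far to replace the endpoint with scheduled samples alone. The protocol defines the outcome as infection or colonisation, and dropping clinical cultures would largely remove infection. Day-28 and day-60 samples are also lost through death and telephone visits. Protocol Appendix B lists the weekly and follow-up samples under the microbiome study and a respiratory culture only at enrolment, although Protocol sections 4 and 7.7 indicate that colonising bacteria are cultured.

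These points stand and limit both the size and the remedy. They do not supply the missing allowance for unequal sampling.

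**Conclusion.** The concern holds in a conditional form. As written, SAP 2.6(d) and 8.7 give an MDR comparison that will be biased if the arms differ in how often patients are cultured, and no part of the plan prevents, adjusts for or fully reveals such a difference. The direction is unknown.

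For one extra culture per patient, the spurious gap runs from negligible when detection in carriers is high to about 5 points at 40% detection; 10.5 points is an upper extreme. The stay-length route is small when the day-28 and day-60 samples are nearly complete and grows as they are missed. All of these sizes rest on assumed carriage, detection and culture counts.

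The endpoint is secondary, and the primary non-inferiority conclusion is unaffected. It would also overstate the matter to call lower resistance the main benefit under test: Protocol section 3 asks about it alongside equivalent clinical outcome.

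**What to change.** Keep the protocol-defined composite and add the following to SAP 8.7.

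1. Prespecify a parallel analysis limited to scheduled screening cultures at times common to both arms: the first weekly sample after randomisation, day 28 and day 60. Report sample completeness and deaths by arm at each time. Restricting to screening cultures without fixing the times would leave the length-of-stay route open.
2. Report MDR growth from clinically ordered cultures as a separate result.
3. Give the number of screening and clinical cultures per participant, and per patient-day, by arm.
4. State that a claim of lower resistance will rest on the composite only if the common-time screening analysis agrees, and say beforehand what counts as agreement.

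Before adopting this, confirm that the scheduled stool and respiratory samples are cultured. If few are, the composite leans more heavily on physician-ordered cultures, and items 2 and 3 matter more.

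The cost is SAP wording and a little more analysis. The screening-only analysis will be less precise and is open to selection, because day-28 and day-60 samples are missing for deaths and telephone visits. For that reason it should stand beside the composite and not replace it.
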